10.1.10 Publication policy

- The results of this study may be published or presented at scientific meetings. If this is foreseen, the Investigator agrees to submit all manuscripts or abstracts to the Sponsor before submission. This allows the Sponsor to protect proprietary information and to provide comments.
- The Sponsor will comply with the requirements for publication of study results. In accordance with standard editorial and ethical practice, the Sponsor will generally support publication of multicenter studies only in their entirety and not as individual site data. In this case, a coordinating Investigator will be designated by mutual agreement.
- Authorship will be determined by mutual agreement and in line with International Committee of Medical Journal Editors authorship requirements.

10.2 APPENDIX 2: CLINICAL LABORATORY TESTS

- The tests detailed in [Table 4](#) will be performed by local laboratory.
- Protocol-specific requirements for inclusion or exclusion of participants are detailed in [Section 5](#).
- Additional tests may be performed at any time during the study as determined necessary by the Investigator or required by local regulations

Table 4 - Protocol-required laboratory assessments

Laboratory tests	Parameters
Hematology ^a	Platelet count Hemoglobin Hematocrit White blood cell (WBC) count with differential: Neutrophils Lymphocytes Monocytes Eosinophils Basophils
Clinical chemistry ^a	Urea or urea nitrogen Creatinine and eGFR (MDRD formula ^b) Glucose Potassium Sodium Corrected Calcium Phosphate Chloride Magnesium Bicarbonate ^c Aspartate aminotransferase (AST)/ Serum glutamic-oxaloacetic transaminase (SGOT) Alanine aminotransferase (ALT)/ Serum glutamic-pyruvic transaminase (SGPT) Alkaline phosphatase Total and direct bilirubin Total protein Lactate dehydrogenase (LDH) Albumin Amylase Lipase
Coagulation	International normalized ratio (INR) or Prothrombin Time (PT) (or Activated Partial Thromboplastin Time [aPTT])
Routine urinalysis ^d	Specific gravity, pH, glucose, protein, blood, ketones, and leukocytes by dipstick Microscopic examination (if blood or protein is abnormal)

Laboratory tests	Parameters
Other screening tests	
Follicle-stimulating hormone and estradiol may be used to confirm a postmenopausal state in women not using hormonal contraception or hormonal replacement therapy (HRT)
 
Highly sensitive serum or urine human chorionic gonadotropin (hCG) pregnancy test (as needed for women of childbearing potential)^e
 
Serology (hepatitis B surface antigen [HBsAg], hepatitis C virus antibody), Hepatitis B viral load, HCV RNA level, CD4 counts & HIV viral Load^f
 
Troponin
 
The results of each test must be entered into the e-CRF

NOTES :

- a Blood Chemistry/hematology should be done with an overnight fasting if possible (should not interfere with hydration requirements). It will be performed weekly on D1 pre-dose, D8 and D15 during Cycle 1, then on Day 1 of every cycle up to Cycle 12, then every other cycle during Treatment Phase. During the Observation Period, it will be performed at Follow-Up Visit 1. It can also be performed as clinically indicated. In case of Grade ≥ 3 liver function abnormal tests, additional tests will be repeated every 2-3 days until recovery to baseline value.
- b Modification of Diet in Renal Disease (MDRD) equation: Glomerular filtration rate (mL/min/1.73 m²) = 175 × (Serum Creatinine [mg/dl])-1.154 × (Age)-0.203 × (0.742 if Female) × (1.212 if African American)
- c Bicarbonate or carbon dioxide (venous) (if bicarbonate or carbon dioxide are assessed only on arterial blood at site level, to be done only if clinically indicated)
- d Urinalysis using dipstick for glucose, blood, pH, protein, ketones, leukocytes and microscopic examination (if blood or protein is abnormal), will be performed every 4 cycles during the Treatment period and as clinically indicated.
- e Pregnancy Test: Women of childbearing potential must have a negative urine pregnancy test result within 72 hours prior to first IMP administration of each cycle, at EOT and every 30 (± 7) days until 120 days (for Cohort A, B1, B2, B3, C, and D1) or 60 days (for Cohort D2) after the last dose of study treatment. If urine pregnancy results cannot be confirmed as negative, a serum pregnancy test will be required. Pregnancy tests (serum and/or urine tests) should be repeated if required by local guidelines.
- f Participants with known HIV infection under antiretroviral treatment should have HIV viral load & CD4+ count done at screening to confirm controlled infection. Participants with known HBV hepatitis under treatment must have viral load determined at baseline to document controlled infection. Participants with positive serology against HCV must have determination of HCV RNA levels. The need for additional testing due to positive test results will be at the discretion of the Investigator. HIV, hepatitis B and C serology at screening will be tested in any countries where mandatory as per local requirements (see [Section 10.7](#)).

Investigators must document their review of each laboratory safety report.

10.3 APPENDIX 3: AES AND SAES: DEFINITIONS AND PROCEDURES FOR RECORDING, EVALUATING, FOLLOW-UP, AND REPORTING

10.3.1 Definition of AE

AE definition

- An AE is any untoward medical occurrence in a patient or clinical study participant, temporally associated with the use of study intervention, whether or not considered related to the study intervention.
- NOTE: An AE can therefore be any unfavorable and unintended sign (including an abnormal laboratory finding), symptom, or disease (new or exacerbated) temporally associated with the use of study intervention.

Events meeting the AE definition

- Any abnormal laboratory test results (hematology, clinical chemistry, or urinalysis) or other safety assessments (eg, ECG, radiological scans, vital signs measurements), including those that worsen from baseline, considered clinically significant in the medical and scientific judgment of the Investigator (ie, not related to progression of underlying disease), eg:
 - Leading to IMP discontinuation or modification of dosing, and/or
 - Fulfilling a seriousness criterion, and/or
 - Defined as an AESI
- Exacerbation of a chronic or intermittent pre-existing condition including either an increase in frequency and/or intensity of the condition.
- New conditions detected or diagnosed after study intervention administration even though it may have been present before the start of the study.
- Signs, symptoms, or the clinical sequelae of a suspected drug-drug interaction.
- Signs, symptoms, or the clinical sequelae of a suspected overdose of either study intervention or a concomitant medication.
- “Lack of efficacy” or “failure of expected pharmacological action” per se will not be reported as an AE or SAE. Such instances will be captured in the efficacy assessments. However, the signs, symptoms, and/or clinical sequelae resulting from lack of efficacy will be reported as AE or SAE if they fulfill the definition of an AE or SAE.
- The signs, symptoms, and/or clinical sequelae resulting from lack of efficacy will be reported as AE or SAE if they fulfill the definition of an AE or SAE. Also, “lack of efficacy” or “failure of expected pharmacological action” also constitutes an AE or SAE.

Events NOT meeting the AE definition

- Any clinically significant abnormal laboratory findings or other abnormal safety assessments which are associated with the underlying disease, unless judged by the Investigator to be more severe than expected for the participant’s condition.
- The disease/disorder being studied or expected progression, signs, or symptoms of the disease/disorder being studied, unless more severe than expected for the participant’s condition.
- Medical or surgical procedure (eg, endoscopy, appendectomy): the condition that leads to the procedure is the AE.
- Situations in which an untoward medical occurrence did not occur (social and/or convenience admission to a hospital).
- Anticipated day-to-day fluctuations of pre-existing disease(s) or condition(s) present or detected at the start of the study that do not worsen.

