8.3 ADVERSE EVENTS (AES), SERIOUS ADVERSE EVENTS (SAES) AND OTHER SAFETY REPORTING

The definitions of adverse events (AEs) and serious adverse events (SAEs) can be found in Appendix 3 ([Section 10.3](#)). The definition of AESI is provided in [Section 8.3.8](#).

AE will be reported by the participant (or, when appropriate, by a caregiver, surrogate, or the participant's legally authorized representative if allowed by local regulations).

The Investigator and any qualified designees are responsible for detecting, documenting, and recording events that meet the definition of an AE or SAE and remain responsible for following up AEs that are serious, considered related to the study intervention or study procedures, or that caused the participant to discontinue the study intervention (see [Section 7](#)).

The method of recording, evaluating, and assessing causality of AEs and SAEs and the procedures for completing and transmitting SAE reports are provided in Appendix 3 ([Section 10.3](#)).

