8.3.7 Disease-related events and/or disease-related outcomes not qualifying as AEs or SAEs

Not applicable.

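### Section 10.3.1 gives opposite instructions in adjacent bullets on whether lack of efficacy is an adverse event, and nothing else in the protocol says which one governs

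*Protocol*

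**What the plan says.** Section 8.3 of the master protocol makes the appendix the governing text: "The definitions of adverse events (AEs) and serious adverse events (SAEs) can be found in Appendix 3". Substudy 01 sends the reader back to the master protocol for the same appendix.

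In Section 10.3.1, the list of events that meet the AE definition has two consecutive bullets on lack of efficacy or failure of the expected pharmacological action:

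- The first says that such failure "per se will not be reported as an AE or SAE. Such instances will be captured in the efficacy assessments". It adds that signs, symptoms and sequelae "resulting from lack of efficacy will be reported as AE or SAE if they fulfill the definition of an AE or SAE".
- The second repeats the sentence on signs, symptoms and sequelae, and then says that lack of efficacy "also constitutes an AE or SAE".

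The list that follows, of events that do not meet the AE definition, includes "The disease/disorder being studied or expected progression, signs, or symptoms of the disease/disorder being studied", with an exception for progression that is worse than expected for that participant.

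Section 8.3.7, titled "Disease-related events and/or disease-related outcomes not qualifying as AEs or SAEs", is marked as not applicable.

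**The concern.** The two bullets cannot both be followed. Under the first, a participant whose tumour does not respond has an efficacy outcome and nothing more. Under the second, the same participant has an adverse event, and a serious one if a seriousness criterion is met. The choice is left to the site.

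TEAE and SAE incidence is a secondary endpoint (Section 3, Table 1), and the DMC reviews cumulative safety data across cohorts (Section 9.5). The AE definition sets the numerator of every one of those summaries. The study has no control arm, so inconsistent recording cannot be offset against a comparator. The problem arises when data are entered and SAEs are reported, so an analysis plan could not fully repair it later.

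**Working it through.** The protocol gives no figure to reproduce, so the check sets the texts side by side.

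1. **Can the bullets be read as complementary?** They share the sentence on signs, symptoms and sequelae, and there they agree. They differ only on lack of efficacy itself: the first says it is not reported, the second says it is an AE or SAE. Neither bullet is limited to a product, cohort or country, so no reading satisfies both.

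2. **Is either bullet superseded text?** No. Both stand in the current appendix, not in an amendment log. The repeated sentence suggests that two versions of one bullet were both kept, but that is an inference.

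3. **Does another section decide?**
   - Section 8.3 defers to Appendix 3.
   - Substudy 01 (Section 8.3 and its Appendix 3) defers to the master protocol.
   - Section 8.3.7, where exempt disease-related events could have been listed, has no content.
   - The list of events that are not AEs covers expected progression. It does not mention lack of efficacy or non-response.

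   None of these resolves the conflict. Section 8 allows no waivers, so a site cannot simply set one bullet aside.

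4. **How would an entry travel into the analysis?** Section 9.4.1 defines the treatment-emergent period as first dose to 30 days after last dose. A lack-of-efficacy entry with onset in that period becomes a TEAE and enters the summaries in Section 9.4.3.5. If it is classed as serious, Section 8.3.1 requires reporting within 24 hours.

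5. **How does progression differ from non-response?** Three texts keep expected progression out of the AE counts:
   - the exclusion quoted above;
   - the first item under events meeting the definition, which limits abnormal findings to those not due to progression;
   - the summary of deaths in Section 9.4.3.5, which gives disease progression a category separate from adverse events.

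   Non-response has no such guard.

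6. **Unit of effect.** Substudy 01 Section 9.2 plans about 40 participants. One participant counted or not counted is 1/40 = 2.5 percentage points. How many would be affected depends on site practice, which the protocol does not describe.

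**The case against.** The strongest reply accepts the contradiction but holds that little follows from it. Much of that reply stands. Expected progression is excluded by name, and deaths from progression have their own category. Results are tabulated by preferred term, so a bare lack-of-efficacy term would be visible and could be separated out, although it would still enter the overall TEAE and SAE counts. The quantified trigger for an ad hoc DMC meeting counts only treatment-related events of Grade 3 or higher that do not resolve within 72 hours, and nothing shows that non-response would be graded and attributed that way. The study tests no hypothesis.

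A reader might also infer two stronger things that the protocol does not support.

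- **That deaths from progression would be reported as Grade 5 TEAEs.** A site would have to disregard the exclusion of expected progression and the separate death category. Section 10.3.3 also defines Grade 5 as a death related to an AE.
- **That 65% to 95% of a cohort would carry a lack-of-efficacy event.** The figure comes from Table 9 of Substudy 01, which shows 2 to 14 responders of 40: 40 − 2 = 38 (95%) and 40 − 14 = 26 (65%) without a response. That is a ceiling. It assumes that every site follows the second bullet and that every participant without an objective response is recorded as a treatment failure. Section 9.4.3.3 counts stable disease at 6 months or later as clinical benefit, so some of those participants are not failures by the protocol's own endpoint. Table 9 also illustrates the precision of the interval; it does not forecast the ORR.

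What the reply does not remove is that two sites, each following the text, can record the same non-response differently.

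**Conclusion.** The AE definition is wrong as written. Two current, adjacent bullets in the governing appendix contradict each other on lack of efficacy, and nothing in the protocol at hand resolves it. The consequence is limited to possible inconsistency between sites in recording non-response as an AE or SAE, and so in the secondary safety endpoint and the safety data given to the DMC. Primary ORR is unaffected, and expected progression is largely guarded.

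The extent cannot be quantified beyond 2.5 percentage points per affected participant in a cohort of 40. The conclusion about the text needs no numerical assumption. The conclusion about the data assumes only that some sites act on the second bullet.

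**What to change.** Delete the second bullet and keep the first. The first already requires reporting of signs, symptoms and sequelae that meet the AE definition, so no safety information is lost. It also agrees with the exclusion of expected progression in Section 10.3.1 and with the death categories in Section 9.4.3.5.

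Tell sites of the correction and query existing entries recorded only as lack of efficacy. Do not withdraw them automatically: an entry may describe a sequela that qualifies as an AE, or progression worse than expected, which Section 10.3.1 does not exclude. Both should be retained.

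The cost is a short wording correction plus a site memo. Because this is the master protocol's AE definition, the correction goes through the amendment route in Section 10.1.1: IRB/IEC approval, and health authority approval if the amendment is classed as substantial. It could be carried in the next amendment.

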10.3.2 Definition of SAE

An SAE is defined as any adverse event that, at any dose:

A) Results in death

B) Is life-threatening

The term “life-threatening” in the definition of “serious” refers to an event in which the participant was at risk of death at the time of the event. It does not refer to an event, which hypothetically might have caused death, if it were more severe.

C) Requires inpatient hospitalization or prolongation of existing hospitalization

In general, hospitalization signifies that the participant has been admitted (usually involving at least an overnight stay) at the hospital or emergency ward for observation and/or treatment that would not have been appropriate in the physician’s office or outpatient setting. Complications that occur during hospitalization are AEs. If a complication prolongs hospitalization or fulfills any other serious criteria, the event is serious. When in doubt as to whether “hospitalization” occurred or was necessary, the AE should be considered serious.

Hospitalization for elective treatment of a pre-existing condition that did not worsen from baseline is not considered an AE.

D) Results in persistent or significant disability/incapacity

- The term disability means a substantial disruption of a person’s ability to conduct normal life functions.
- This definition is not intended to include experiences of relatively minor medical significance such as uncomplicated headache, nausea, vomiting, diarrhea, influenza, and accidental trauma (eg, sprained ankle) which may interfere with or prevent everyday life functions but do not constitute a substantial disruption.

E) Is a congenital anomaly/birth defect

F) Other situations:

- Medical or scientific judgment should be exercised by the Investigator in deciding whether SAE reporting is appropriate in other situations such as significant medical events that may jeopardize the participant or may require medical or surgical intervention to prevent one of the other outcomes listed in the above definition. These events should usually be considered serious.

Note: The following list of medically important events is intended to serve as a guideline for determining which condition has to be considered as a medically important event. The list is not intended to be exhaustive:

- Intensive treatment in an emergency room or at home for:
 - Allergic bronchospasm
 - Blood dyscrasias (ie, agranulocytosis, aplastic anemia, bone marrow aplasia, myelodysplasia, pancytopenia, etc)

- Convulsions (seizures, epilepsy, epileptic fit, absence, etc).
- Development of drug dependence or drug abuse
- Suicide attempt or any event suggestive of suicidality
- Syncope, loss of consciousness (except if documented as a consequence of blood sampling)
- Bullous cutaneous eruptions

The purpose of the seriousness criteria listed above is to guide regulatory reporting obligations by the Sponsor. The Sponsor is required to expedite serious unexpected adverse reactions to regulatory health authorities and Investigators.

10.3.3 Recording and follow-up of AE and/or SAE

AE and SAE recording

- When an AE/SAE occurs, it is the responsibility of the Investigator to review all documentation (eg, hospital progress notes, laboratory reports, and diagnostics reports) related to the event.
- The Investigator will then record all relevant AE/SAE information in the e-CRF.
- It is **not** acceptable for the Investigator to send photocopies of the participant's medical records to the Sponsor's representative in lieu of completion of the AE/SAE e-CRF page.
- There may be instances when copies of medical records for certain cases are requested by the Sponsor's representative. In this case, all participant identifiers, with the exception of the participant number, will be redacted on the copies of the medical records before submission to the Sponsor's representative.
- The Investigator will attempt to establish a diagnosis of the event based on signs, symptoms, and/or other clinical information. Whenever possible, the diagnosis (not the individual signs/symptoms) will be documented as the AE/SAE.

Assessment of intensity

The Investigator will make an assessment of intensity for each AE and SAE reported during the study and assign it to 1 of the following categories, as per NCI CTCAE V5.0 definitions (except for ICANS and CRS that will be graded using ASTCT criteria integrated with central laboratory cytokine results):

- Grade 1 Mild; asymptomatic or mild symptoms; clinical or diagnostic observations only; intervention not indicated.
- Grade 2 Moderate; minimal, local or noninvasive intervention indicated; limiting age-appropriate instrumental activities of daily living (ADL)*.
- Grade 3 Severe or medically significant but not immediately life-threatening; hospitalization or prolongation of hospitalization indicated; disabling; limiting self-care ADL**.

- Grade 4 Life-threatening consequences; urgent intervention indicated.
- Grade 5 Death related to AE.

An event is defined as “serious” when it meets at least 1 of the predefined outcomes as described in the definition of an SAE, NOT when it is rated as severe.

*Instrumental ADL refer to preparing meals, shopping for groceries or clothes, using the telephone, managing money, etc.

**Self-care ADL refer to bathing, dressing and undressing, feeding self, using the toilet, taking medications, and not bedridden.

Assessment of causality

- The Investigator is obligated to assess the relationship between study intervention and each occurrence of each AE/SAE.
- A "reasonable possibility" of a relationship conveys that there are facts, evidence, and/or arguments to suggest a causal relationship, rather than that a relationship cannot be ruled out.
- The Investigator will use clinical judgment to determine the relationship.
- Alternative causes, such as underlying disease(s), concomitant therapy, and other risk factors, as well as the temporal relationship of the event to study intervention administration will be considered and investigated.
- The Investigator will also consult the Investigator's Brochure (IB) and/or Product Information, for marketed products, in his/her assessment.
- For each AE/SAE, the Investigator **must** document in the medical notes that he/she has reviewed the AE/SAE and has provided an assessment of causality.
- There may be situations in which an SAE has occurred and the Investigator has minimal information to include in the initial report to the Sponsor's representative. However, **it is very important that the Investigator always make an assessment of causality for every event before the initial transmission of the SAE data to the Sponsor's representative.**
- The Investigator may change his/her opinion of causality in light of follow-up information and send an SAE follow-up report with the updated causality assessment.
- The causality assessment is one of the criteria used when determining regulatory reporting requirements.

Follow-up of AEs and SAEs

- The Investigator is obligated to perform or arrange for the conduct of supplemental measurements and/or evaluations as medically indicated or as requested by the Sponsor's representative to elucidate the nature and/or causality of the AE or SAE as fully as possible. This may include additional laboratory tests or investigations, histopathological examinations, or consultation with other health care professionals.
- If a participant dies during participation in the study or during a recognized follow-up period, if available the Investigator will provide the Sponsor's representative with a copy of any post-mortem findings including histopathology.
- New or updated information will be recorded in the originally submitted documents.
- The Investigator will submit any updated SAE data to the Sponsor within 24 hours of receipt of the information.

